 - t. A general ophthalmologist can perform the examination, although a retinal specialist would be preferred wherever possible. A complete ophthalmoscopy and OCT assessment should be performed according to the SoA. Site should retain a copy of the OCT result and the ophthalmologist report. For participants with a suspicion of new onset of macular edema and/or retinopathy, along with evaluation using ophthalmoscopy and OCT, additional testing should be considered at the discretion of the ophthalmologist (eg, general retinal examinations, including eye history, visual acuity, dilated ophthalmoscopy).
 - u. Participants will receive a stool sampling kit at a previous visit and be asked to collect a stool sample within 24 hours before the next visit. Participants are to bring stool samples to the clinic.
- [REDACTED]

- x. PK samples will be collected (measuring trough concentrations) after completion of vital sign assessments and ECGs. When study drug is administered at the clinic, PK sample will be collected predose. On Day 1 only, PK samples will also be collected at 2, 4, and 6 hours (\pm 10 minutes) postdose (see [Table 10](#)).
- y. Sigmoidoscopy is sufficient at both Screening and Visit 7. Colonoscopy can be performed if a surveillance colonoscopy is needed or based on the clinical judgment of the Investigator.
- z. Participants will begin eDiary entries beginning on the first day of Screening after diary training is completed. The eDiary should be completed daily to capture data, including daily SF and RB (the 2 patient-reported outcome measures of the MMS), and study drug administration. Study center personnel should review the diary data at every visit at the timepoints in the table and in between visits via EDC to confirm compliance with eDiary completion. In addition, the RB score should be assessed during the Screening Period to ensure the RB score will meet eligibility criteria prior to performing the endoscopy.
- aa. The MMS will be calculated electronically during Screening for eligibility and at Visit 7 for determination of clinical response. The subscores for RB and SF are derived from the participant eDiary entries using the scores from the 3 most recent consecutive days within the 7 days prior to the day of bowel preparation, averaged and rounded to the nearest integer.

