8.3.2 Endoscopic Biopsies

Per the inclusion criteria ([Section 5.1](#)), a histopathology report supporting the diagnosis of UC must be available in the source documents prior to randomization. If a histopathology report is not available, the Screening endoscopy may serve as such with histology evaluated at the local histology laboratory.

Biopsies will be obtained at each endoscopy to support assessment of the histopathology endpoints [REDACTED] Up to 4 biopsy pairs (ie, total of 8) will be collected from the most affected area 15 to 25 cm from the anal verge. For participants with proctitis only at baseline, biopsies should be taken 8 to 10 cm from the anal verge.

The original location (colonic segment) of biopsy specimens acquired at Screening must be clearly indicated. Detailed instructions for endoscopic biopsies (eg, number of biopsies, anatomic site, normal or inflamed mucosa) can be found in the Laboratory Manual.

Biopsy samples will be processed by a central laboratory, and histopathologic scoring using the Geboes, Robarts, and Nancy histopathology indices will be performed by a blinded central reader ([Appendix 7](#)).

Biopsy specimen transfer, processing, slide preparation, and digitization of slides for histopathologic scoring procedures will be detailed in a Histopathology Manual. [REDACTED] This will be further delineated in the Laboratory Manual. Histopathology results will not be made available to study sites.

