^b When endoscopy occurs: SF and RB scores are computed using a 7-day look back window whose ending Study Day is immediately prior to the first day of bowel preparation, and these SF and RB scores are attached to the endoscopy. If no bowel preparation is performed for a given endoscopy, the 7-day look back window ends at the Study Day immediately prior to the endoscopy. If the endoscopy occurs outside of both Visit 1/Baseline and Visit 7 analysis windows for endoscopy, the SF, RB, ES, and histopathology data for the endoscopy are not associated with any analysis visit and are listed only. If the endoscopy occurs inside either the Visit 1/Baseline or Visit 7 endoscopy analysis window, the SF, RB, ES, and histopathology data are associated with Visit 1/Baseline or Visit 7 as appropriate. If multiple endoscopies are associated with the same Visit 1 or Visit 7 analysis visit window, the following sequential steps will be applied to choose a unique endoscopy to associate with the analysis visit: [i] endoscopies with missing ES scores are dropped from consideration and, [ii] if there are remaining endoscopies to choose from, the most recent endoscopy is kept. After determining a unique endoscopy to associate with the analysis visit, if the 7-day look back window overlaps with a previous set of endoscopy and/or bowel preparation dates, the eDiary SF and RB values for those overlapping dates will be set to missing for computational purposes.

^c For a given post-baseline analysis visit, if no endoscopy is associated with that analysis visit SF and RB will be computed using a 7-day look back window whose ending Study Day is immediately prior to the site visit closest to the Ideal Study Day when a within-window site visit exists. If two site visits are equidistant from the Ideal Study Day, the earlier site visit is chosen. If no site visit is associated with the given post-baseline analysis visit, SF and RB will be not be computed for that visit. If the 7-day look back window overlaps with a previous set of endoscopy and/or bowel preparation dates, the eDiary SF and RB values for those overlapping dates will be set to missing for computational purposes.

^d Post-baseline ET and Unscheduled visits may include endoscopy and analysis visit windows are applied to ET and Unscheduled visit data in a manner identical to that of other visits. Endoscopy data from ET and Unscheduled visits may not be associated with any analysis visit other than Visit 7. Endoscopy

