16. EFFICACY

Controlled efficacy analyses are limited to the Induction Treatment Period. Efficacy endpoints may be computed for LTE and OLE study visits, but all hypothesis testing will be uncontrolled, resulting in nominal p-values and CIs only.

The study is designed to show superiority of VTX002 60 mg to placebo for the primary efficacy endpoint at Induction Week 13. Four key secondary endpoints are defined for this study and VTX002 30 mg is an important additional active drug dose of interest. Across the primary endpoint and key secondary endpoints, a total of ten (10) Induction Week 13 controlled hypothesis tests involving the two randomized VTX002 doses and placebo are planned. The family-wise error rate will be maintained at $\alpha = 0.05$ – see [Section 10.3](#) for details.

All controlled efficacy analyses (Week 13, Induction) will be primarily based on participant stratum at randomization (see [Section 10.2](#)) according to IWRS and for the FAS. Participants having MMS = 4 at baseline will be excluded from all efficacy analyses except the sensitivity analysis described in [Section 16.1.5](#). Additional sensitivity and/or supportive analyses will be performed as described elsewhere in this section. For composite scores such as MMS, if one or more components is missing from an analysis visit window the composite score is missing.

Blinded study team review will be used prior to Induction interim database lock and unblinding, to attribute a known Induction Week 13 non-response to participants having specific on-study experiences. Participants will be classified as non-responders in all responder-based efficacy analyses, including the primary endpoint, at all timepoints subsequent to the experience of the earliest of any of the following intercurrent events:

- Missed Visit 7 Week 13 endoscopy for participants eligible to have Visit 7 Week 13 endoscopy
- Discontinuation of the study during the Induction Treatment Period for either disease worsening or treatment-emergent adverse event having a preferred term indicating ulcerative colitis (UC)

- Exposure to rescue therapy for UC. See Appendix IV, [Section 25](#).

For a given participant, if efficacy outcomes (as opposed to components of outcomes) are available subsequent to an intercurrent event, they will be flagged as such. Participants may be included in the PP Set as long as other Per Protocol criteria are not violated.

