Repeated measures Induction/LTE data on the same endpoints (clinical remission, endoscopic improvement, endoscopic remission, histologic improvement (Geboes), and histologic remission (Geboes) at Weeks 4, 8, 10, 13, 18, 26, 36, and 52 will be analyzed. This will be done using repeated measurements logistic regression specifying the distribution as binomial, the link function as logit and randomization stratification factors added as covariates in addition to randomized treatment. Two summaries will be provided: summary for the Induction Treatment Period will include only data from Weeks 4, 8, 10 and 13, whereas a comprehensive summary for both Induction and LTE will include data through Week 52. Sample SAS code is presented below:

[REDACTED]

[REDACTED]

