28. APPENDIX VII. DETERMINATION OF SAMPLE SIZE

Based on literature data review, the expected proportion of clinical remission at Induction Week 13 is 28% for VTX002 60 mg and 8% for placebo (Sandborn 2016; Sandborn 2020). Under these assumptions, and with a 1:1 randomization ratio, 2-group chi-squared test, and two-sided significance level of 5%, a sample of 57 participants per treatment group will be sufficient to achieve at least 80% power. Adding a 10% inflation for dropouts results in 63 participants per treatment group and 189 participants in total.

Software

SAS (version 9.4; SAS Institute Inc.; Cary, NC, USA).

Input & Output

Fixed Scenario Elements	
Distribution	Asymptotic normal
Method	Normal approximation
Number of Sides	2
Alpha	0.05
Group 1 Proportion	0.08
Group 2 Proportion	0.28
Nominal Power	0.8
Null Proportion Difference	0

Computed N per Group	
Actual Power	N per Group
0.802	57

29. APPENDIX VIII. RELATIONSHIP OF INTERCURRENT EVENTS TO NON-RESPONDER IMPUTATION, MULTIPLE IMPUTATION, COPY REFERENCE IMPUTATION, AND TIPPING POINT

Table 12. Relationships Between Various Types of Imputation and Data Missingness

Type of Occurrence	Visits Affected	Effect of Protocol Deviations	Primary Analysis of Primary, Key Secondary, and Other Secondary Endpoints	Multiple Imputation	Copy Reference	Tipping Point
Intercurrent Event	All visits on/after intercurrent event, regardless of data missingness for other reasons . Intercurrent event handling takes priority over missing data handling.	An intercurrent event is a major protocol deviation. As long as other deviations don't prevent the participant from being Per Protocol, they will be included in the PP Set.	Non-responder imputation	Non-responder imputation	Non-responder imputation	Non-responder imputation
Missing Data	Visits w/ efficacy endpoints having missing values in one or more endpoint components.	As long as there are no intercurrent events, missing data is handled per this row in the table.	Non-responder imputation	Multiple imputation	Copy reference imputation	Tipping point imputation

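### The SAP's repeated-measures logistic model covers eight weeks, but its five endpoints need endoscopy or biopsy, scheduled only at Weeks 13 and 52, so the Induction model has one observed visit.

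*SAP*

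**What the plan says.** SAP 16.3 names five endpoints for a repeated-measures logistic regression (binomial, logit link): clinical remission, endoscopic improvement, endoscopic remission and two histologic endpoints. The sentence that sets the weeks ends: "histologic improvement (Geboes), and histologic remission (Geboes) at Weeks 4, 8, 10, 13, 18, 26, 36, and 52 will be analyzed". Two summaries are planned. The "summary for the Induction Treatment Period will include only data from Weeks 4, 8, 10 and 13", and the other runs through Week 52. The model terms named in the text are "randomization stratification factors added as covariates in addition to randomized treatment"; the sample code is redacted. Protocol 9.4.1.3 has the same plan, with endoscopic response in place of endoscopic improvement.

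On when ES and Geboes exist:
- Protocol Table 1 schedules endoscopy and biopsy at Screening, Week 13 and early termination (ET). Its footnote y says "Sigmoidoscopy is sufficient at both Screening and Visit 7". Week 10 is a planned phone call.
- Protocol Table 2 (LTE) schedules them at Week 52 and at ET, the latter required only for discontinuation at or after Week 26.
- Geboes depends on endoscopy: "Biopsies will be obtained at each endoscopy to support assessment of the histopathology endpoints" (Protocol 8.3.2).
- SAP Table 3 gives endoscopy a Baseline window and a Visit 7 window only. Footnote d adds: "Endoscopy data from ET and Unscheduled visits may not be associated with any analysis visit other than Visit 7".

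On imputation, SAP Section 16 has participants with an intercurrent event "classified as non-responders in all responder-based efficacy analyses, including the primary endpoint, at all timepoints subsequent to the experience of the earliest" such event. SAP Appendix VIII, Table 12, states: "Intercurrent event handling takes priority over missing data handling".

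The Statistical Methods part of the protocol synopsis assigns categorical repeated measures at these same eight weeks to symptomatic response and symptomatic remission.

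**The concern.** A repeated-measures model needs repeated measurements. At Weeks 4, 8, 10, 18, 26 and 36 none of the five endpoints can be determined from scheduled assessments, so the analysis cannot be carried out at the weeks stated.

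Three things follow.
- The Induction output would be described as longitudinal while resting on one visit.
- The general non-responder rules could put imputed failures into weeks where success was impossible to observe. Participants with early events would then count more than once.
- The endpoints that do have data at all eight weeks have lost the longitudinal analysis that the synopsis gives them, and SAP Section 18, which lists departures from the protocol, does not mention it.

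**Working it through.** **1. What each endpoint needs (SAP 7.5 and Table 9).** Clinical remission needs ES, RB and SF. Endoscopic improvement and endoscopic remission need ES. Histologic improvement and histologic remission need Geboes. Under SAP 9.6, a composite with a missing component is missing.

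**2. Cells with scheduled data.**
- All weeks: 5 endpoints × 8 weeks = 40 cells. Weeks 13 and 52 supply 5 × 2 = 10, or 25%.
- Induction: 5 × 4 = 20 cells. Week 13 supplies 5 × 1 = 5.
- ET and unscheduled endoscopies in Induction map to Visit 7 or are listed only, so they add nothing at Weeks 4, 8 or 10.

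**3. The Induction model on observed data.** The illustration uses 63 per arm (planned size) and 18 versus 5 responders at Week 13, close to the planned 28% and 8%, without strata. The odds ratio is (18/45)/(5/58) = 4.64, with log odds ratio 1.535 and SE 0.543. A GEE fit to the same 126 records returns the same values, and there is no within-participant correlation to estimate.

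**4. Intercurrent-event rule read literally at early weeks.** Rescue therapy, or discontinuation for disease worsening or a UC adverse event, can happen before Week 10; a missed Week 13 endoscopy cannot. Assume 12 Week 13 non-responders had such an event, each adding failure records at Weeks 8 and 10. That gives 126 + 24 = 150 records. With independence and no visit term:
- 4 active, 8 placebo: (18/53)/(5/74) = 5.03
- 6 and 6: (18/57)/(5/70) = 4.42
- 8 and 4: (18/61)/(5/66) = 3.90

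| Early events, active vs placebo | Independence | Exchangeable | Visit as factor |
|---|---|---|---|
| none | 4.64 | 4.64 | 4.64 |
| 4 vs 8 | 5.03 | 4.88 | 4.64 |
| 6 vs 6 | 4.42 | 4.51 | 4.64 |
| 8 vs 4 | 3.90 | 4.25 | 4.64 |

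A visit factor (fitted under independence) removes the effect, because the added weeks hold failures only.

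**5. Missing-data row of Table 12 read literally as well.** Every participant then becomes a failure at Weeks 4, 8 and 10. That is 126 × 4 = 504 records, and without a visit term the odds ratio is (18/234)/(5/247) = 3.80 (log odds ratio 1.335, SE 0.488). With a visit term the treatment estimate returns to 4.64, but the visit terms are separated (standard errors above 30,000).

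**6. The alternative in the synopsis.** Symptomatic response and remission use RB and SF from the daily eDiary, so all 8 weeks, including all 4 in Induction, have planned diary data. The SAP gives these endpoints a CMH test per timepoint (Table 6, Sections 16.3 and 16.4) and no longitudinal model.

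**The case against.** The strongest reply is that the general imputation rules were never meant to reach Weeks 4 to 10. The five endpoints are defined at Week 13, and a week with no planned endoscopy is arguably not a visit for an endoscopic endpoint. On that reading neither row of Table 12 applies, the model is simply a Week 13 logistic regression, and no distortion arises. That reading is reasonable, but the SAP does not state it, and Section 16 covers all responder analyses at all later timepoints.

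The odds ratios in the illustration also rest on assumed event counts. With 2 versus 2 early events the independence value is (18/49)/(5/62) = 4.56; with 1 versus 2 it is (18/47)/(5/62) = 4.75. The largest downward shift among the 12-event cases, 4.64 to 3.90, is ln(4.64/3.90) = 0.17 on the log scale, about a third of the standard error. A visit term would remove it, and the redacted code may contain one. This stands: the figures show direction and possible size, not an established bias.

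In the LTE, an ET endoscopy after Week 26 could fall near Week 36, and the SAP gives no LTE windows. So 10 of 40 counts scheduled data only. The Induction count of 5 of 20 is firm.

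Finally, the consequence is low. All five endpoints have stratified CMH tests at Week 13, the protocol calls this model exploratory, and no multiplicity control applies. That is correct and sets the rating. It does not make the stated analysis feasible.

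**Conclusion.** The concern holds and is minor. As written, the model cannot be run at six of its eight weeks on scheduled data, and the Induction version has one observed visit. This follows from the schedules, endpoint definitions and windowing rules, and does not depend on the redacted code.

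Any numerical distortion is conditional on three things: a literal reading of the imputation rules, the number and split of early events, and the absence of a visit term. Under the assumptions shown, the odds ratio lies between 3.80 and 5.03, against 4.64 from Week 13 alone. Primary and key secondary inference is unaffected.

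**What to change.** Before the interim database lock:
- Reconcile the synopsis, Protocol 9.4.1.3 and SAP 16.3 on which endpoints the categorical repeated-measures model serves, and record any departure in SAP Section 18.
- Limit the five ES- and Geboes-based endpoints to Week 13 for Induction and to Weeks 13 and 52 for the combined summary. Note that Week 52 data come mainly from Week 13 clinical responders, because clinical response governs entry to the LTE.
- State that weeks without a scheduled endoscopy contribute no records for these endpoints, whether through missing-data or intercurrent-event imputation.
- If a longitudinal categorical model is kept, apply it to symptomatic remission and symptomatic response, and name visit as a model term in the text.
- Settle how RB and SF are derived at Week 10, which that model would need. Visit 6 is a phone call. With no site visit, SAP Table 3 footnote c leaves the scores uncomputed, while SAP 10.3 looks back from the Ideal Study Day.

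The cost is a few sentences in the SAP. No new data are required: the diary data are already collected and the Week 13 CMH tests are already planned.

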16.4 Exploratory Efficacy

The endpoints described here will be analyzed separately, as appropriate, for the Induction Treatment Period, Long-Term Extension Treatment Period (LTE), and Open-Label Extension (OLE). In general, when an endpoint refers to Induction Study Period visits, that endpoint will be included in the Induction Period Analysis, but restricted to visits associated with the Induction Study Period. For example, CRP change from baseline analysis will be included in the Induction Period Analysis, but restricted to Weeks 1, 4, 8, and 13. LTE and OLE analyses for the same endpoint may differ not only with respect to the participant set but also with respect to statistical methodology.

- Proportion of participants with histologic remission at Week 13 using RHI
- Proportion of participants with histologic remission at Week 13 using NHI
- Proportion of participants with histologic improvement at Week 13 using RHI
- Proportion of participants with histologic improvement at Week 13 using NHI
- Proportion of participants with clinical remission after 52 weeks of treatment
- Proportion of participants with clinical remission after 13 and 52 weeks of treatment
- Proportion of participants with symptomatic remission at Weeks 18, 26, 36, and 52
- Proportion of participants with endoscopic remission with histologic remission after 52 weeks of treatment
- Proportion of participants with endoscopic improvement-histologic remission after 52 weeks of treatment
- Proportion of participants with endoscopic and clinical remission after 52 weeks of treatment

- Proportion of participants with endoscopic remission, histologic remission, and clinical remission after 52 weeks of treatment
- Proportion of participants with HEMI after 52 weeks of treatment
- Proportion of participants with clinical response after 52 weeks of treatment
- Proportion of participants with symptomatic response at Weeks 18, 26, 36, and 52
- Proportion of participants with symptomatic response at OLE Week 13, and at each additional OLE visit
- Proportion of participants with any decrease from baseline in Geboes Index score at Week 52
- Change from baseline in FCP at Weeks 1, 4, 8, 13, 26, 36, 52, and at visits during the OLE
- Change from baseline in CRP at Weeks 1, 4, 8, 13, 26, 36, 52, and at visits during the OLE
- Change from baseline in PMS at Weeks 4, 8, 13, 18, 26, 36, 52, and at visits during the OLE
- Change from baseline in total MCS at Week 52
- Change from baseline in IBDQ score at Weeks 13 and 52
- Change and percentage change from baseline in lymphocyte counts at Weeks 1, 4, 8, 13, 26, 36, and 52
- Change and percentage change from baseline in Rectal Bleeding at Weeks 1, 4, 8, 10, 13, 18, 26, 36, and 52
- Change and percentage change from baseline in Stool Frequency at Weeks 1, 4, 8, 10, 13, 18, 26, 36, and 52

The first fifteen exploratory endpoints will be handled as responder analyses and analyzed similarly to the primary endpoint, per timepoint, using the CMH test with the same as-randomized stratification factors. The FAS set will be used for this purpose and treatment group comparisons (VTX002 60 mg vs placebo; VTX002 30 mg vs placebo) will be as-randomized. No adjustment for multiplicity will be made and the nominal Type 1 error rate for each hypothesis test is $\alpha=0.05$.

The last eight exploratory endpoints are quantitative. [Table 7](#) describes the analyses and analysis sets to be used for treatment group comparisons for these endpoints.

For the parameters listed in [Table 7](#), when Summary Statistics are indicated absolute values, change from baseline, and percent change from baseline will be summarized. The analysis set in the table denotes how treatment group is handled in these summaries. Additionally, figures for mean (SD) absolute value - time curve during study will be created for the following parameters:

CRP, lymphocyte counts, and neutrophil counts using normalized pooled data from both central laboratories. Separate figures will be generated for induction, LTE and OLE Treatment Periods.

Table 7. Quantitative Exploratory Endpoints and Analysis Sets

Parameter	Timepoint	Comparison	Methodology	Analysis Set
FCP (central laboratory)	Induction treatment: Weeks 1, 4, 8, 13	VTX002 60 mg vs Placebo	MMRM ^a , Summary Statistics ^b	FAS
		VTX002 30 mg vs Placebo		FAS
	LTE/OLE: Weeks 26, 36, 52 and each visit during the OLE	VTX002 60 mg vs Placebo		FAS
		VTX002 30 mg vs Placebo		FAS
CRP (central laboratory)	Induction treatment: Weeks 1, 4, 8, 13	VTX002 60 mg vs Placebo		FAS
		VTX002 30 mg vs Placebo		FAS
	LTE/OLE: Weeks 26, 36, 52 and each visit during the OLE	VTX002 60 mg vs Placebo		FAS
		VTX002 30 mg vs Placebo		FAS
PMS	Induction treatment: Weeks 4, 8, 13	VTX002 60 mg vs Placebo	FAS, PP	
		VTX002 30 mg vs Placebo	FAS-ET	
	LTE/OLE: Weeks 18, 26, 36, 52 and each visit during the OLE	VTX002 60 mg vs Placebo	FAS-ET	
		VTX002 30 mg vs Placebo	FAS-ET	
Total MCS	LTE: Week 52	No formal comparisons, VTX002 60 mg, VTX002 30 mg, and placebo presented by visit	Summary Statistics ^b	FAS ET
IBDQ	Induction treatment: Week 13			FAS
	LTE: Week 52			FAS ET
Lymphocyte counts (central laboratory)	Induction treatment: Weeks 1, 4, 8, 13			FAS
	LTE/OLE: Weeks 26, 36, and 52			FAS ET
Stool Frequency	Induction treatment: Weeks 0, 1, 4, 8, 10, 13			FAS
	LTE/OLE: Weeks 18, 26, 36, 52 and each visit during the OLE			FAS ET

Parameter	Timepoint	Comparison	Methodology	Analysis Set
Rectal Bleeding	Induction treatment: Weeks 0, 1, 4, 8, 10, 13			FAS
	LTE/OLE: Weeks 18, 26, 36, 52 and each visit during the OLE			FAS ET
Symptomatic Response and Symptomatic Remission	Induction treatment: Week 13			FAS
	LTE/OLE: Weeks 18, 26, 36, and 52			FAS ET

^a Mixed Model for Repeated Measures, used to model change from baseline for Induction Treatment Period separately from the pooled visits across both the Induction and LTE study periods. MMRM generates statistical comparisons between treatment groups, by visit and overall.

^b Summary statistics are produced by visit for each treatment group and statistical comparisons between treatment groups are not produced.

Where mixed models with repeated measurements (MMRM) are indicated in [Table 7](#), the analysis will be applied to change from baseline in FCP (separately for Cerba and LabCorp central laboratories, Weeks 1, 4, 8, 13, 26, 36, and 52), CRP (Weeks 1, 4, 8, 13, 26, 36, and 52) and PMS (Weeks 4, 8, 13, 26, 36, and 52). The Induction Treatment Period will be handled separately from the pooled visits across both the Induction and LTE study periods. For the Induction Treatment Period, MMRM model(s) will include data from weeks 1, 4, 8 and 13. For the combined Induction and LTE study periods, MMRM model(s) will include all available data from scheduled visits across both study periods.

No imputation of missing results will be done. If a participant has any missing data whatever non-missing data is available for that participant will be used in the MMRM.

Least square means for both change from baseline within treatment group and difference between treatment groups with respect to the outcome variable, together with standard errors, 95% CIs, and pairwise treatment group p-values (VTX002 60 mg versus placebo; VTX002 30 mg versus placebo) will be reported, by visit. Stratification factors will be added as covariates and will be handled as-randomized in all cases regardless of the analysis set being used.

Sample SAS code is presented below:

```

[REDACTED SAS CODE]
    
```

An Unstructured Covariance structure will be used in Proc Mixed. If that fails to converge, Autoregressive Covariance structure will be used. If that fails to converge, Compound Symmetry will be used. The contain method of computing degrees of freedom will be applied.

